
Exclusion Criteria:
	
An individual fulfilling any of the following criteria is to be excluded from trial enrollment:
 
 1) Subject is pregnant, or lactating, or of childbearing potential (to be considered of non-childbearing potential, a female must be pre-menarche, surgically sterile, or using an effective method of contraception or abstinence from at least 4 weeks prior to the first vaccination until at least 4 weeks after the last vaccination)* 2) Participation at the time of study enrollment (or in the 4 weeks preceding the first trial vaccination) or planned participation during the present trial period in another clinical trial investigating a vaccine, drug, medical device or medical procedure 3) Self-reported or suspected congenital or acquired immunodeficiency; or receipt of immunosuppressive therapy such as anti-cancer chemotherapy or radiation therapy within the preceding 6 months; or long-term systemic corticosteroid therapy (prednisone or equivalent for more than 2 consecutive weeks within the past 3 months) 4) Self-reported systemic hypersensitivity to any of the vaccine components, or history of a life-threatening reaction to the vaccine used in the trial or to a vaccine containing any of the same substances** 5) Chronic illness that, in the opinion of the Investigator, is at a stage where it might interfere with trial conduct or completion*** 6) Receipt of blood or blood-derived products in the past 3 months, which might interfere with assessment of the immune response 7) Planned receipt of any vaccine in the 4 weeks following any trial vaccination 8) Previous vaccination against dengue disease with either the trial vaccine or another vaccine 9) Deprived of freedom by an administrative or court order, or in an emergency setting, or hospitalized involuntarily 10) Current alcohol abuse or drug addiction that, based on Investigator’s judgment, may interfere with the subject’s ability to comply with trial procedures. 11) Identified as a site employee of the Investigator, with direct involvement in the proposed study or other studies under the direction of that Investigator or study center, as well as family members (ie, immediate, husband, wife, and their children, adopted or natural) of the employees or the Investigator 12) A prospective subject must not be included in the study until the following conditions and/or symptoms are resolved: 
 • Febrile illness (temperature $\geq 38.0^{\circ}\text{C}$) or moderate or severe acute illness/infection (according to Investigator’s judgment) on the day of vaccination. • Receipt of any vaccine in the 4 weeks preceding the first trial vaccination 
* For pre-menarche females, the young female subjects declare if they have not yet started menstruation; if a young female subject reaches menarche during the study, she is to be considered as a woman of childbearing potential from that time forward.
 
** The components of CYD dengue vaccine and placebo are listed in Section 6.1 and in the Investigator’s Brochure.
 
*** Chronic illness may include, but is not limited to, cardiac disorders, renal disorders, auto-immune disorders, diabetes, psychiatric disorders, or chronic infection.

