--

	
Analysis of covariance (ANCOVA) will be used to compare the post booster mean response of neutralizing Ab levels against each dengue virus serotype of two groups (eg, Group 2 versus Group 1 or Group 3 versus Group 1) controlling for the baseline neutralizing Ab levels against each dengue virus serotype, in subjects seropositive at baseline. Further details regarding the ANCOVA model will be outlined in the SAP.
 
AIT Subset:
 
• For categorical data, the number and percentage of subjects above or equal to the lower limit of detection (LLOD), and the 95% CI of the percentage of the subjects.• For continuous data, Log10: mean and standard deviation; geometric mean, 95% CI of the geometric mean and quartiles, minimum and maximum value.
--	--

Table of Procedures – STAGE I and STAGE II

Visit Number (V)	STAGE I							STAGE II*								
	V01	V02	V03	V04	V05	V06	6M FU (PC7)†	V06_Inf	V07 (Y1)	V07 (Y2)	V08 (Y1/Y2) (AIT only)	V09 (Y1/Y2) (AIT only)	V10 (Y1/Y2)	6M FU (PC)‡		
Trial timelines (Days/Months)	V01	V01+ 28d	V01+ 180d	V03+ 28d	V01+ 365d	V05+ 28d	last inj + 6M		V05+ 12M	V05+ 24M	V07+ 7d	V07+ 14d	V07+ 28d	V07+ 6M		
Time Windows (Days)		+14d	±20d	+14d	±20d	+14d	+20d		+60	+60	+3d	+7d	+14d (+7d for AIT)	+20d		
Informed Consent/Assent	√								√							
Information letter on baseline serostatus								√								
Inclusion/Exclusion Criteria	√															
Demography	√															
Contraindications	√		√		√				Subgroup a: V07 Y1 Subgroup b: V07 Y2							
Significant Medical History	√															
History of YF or JE Infection/Vaccination and/or Dengue Infection	√															
Physical Examination and Temperature§	√	√	√	√	√	√			subgroup a: V07 Y1 subgroup b: V07 Y2		√	√	√			
Urine Pregnancy Test (pre-injection)**	√		√		√											
Concomitant Therapy	√	√	√	√	√	√							√	√	√	
IVRS/IWRS Contact	√		√		√											
Injection	Inj. 1		Inj. 2		Inj. 3				Booster Inj. subgroup a: V07 Y1 subgroup b: V07 Y2							

STAGE I							STAGE II*							
Visit Number (V)	V01	V02	V03	V04	V05	V06	6M FU (PC7)†	V06_Inf	V07 (Y1)	V07 (Y2)	V08 (Y1/Y2) (AIT only)	V09 (Y1/Y2) (AIT only)	V10 (Y1/Y2)	6M FU (PC)‡
Trial timelines (Days/Months)	V01	V01+ 28d	V01+ 180d	V03+ 28d	V01+ 365d	V05+ 28d	last inj + 6M		V05+ 12M	V05+ 24M	V07+ 7d	V07+ 14d	V07+ 28d	V07+ 6M
Time Windows (Days)		+14d	±20d	+14d	±20d	+14d	+20d		+60	+60	+3d	+7d	+14d (+7d for AIT)	+20d

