- ** Urine pregnancy test for females of child-bearing potential; to be considered of non-child-bearing potential, a female must be post-menopausal for at least 1 year, surgically sterile, or using an effective method of contraception or abstinence from at least 4 weeks prior to vaccination and until at least 3 weeks after vaccination
- †† Blood samples planned during vaccination visits will be taken before injection. Baseline YF and JE status will be assessed using PRNT.
- ‡‡ BL6 is to be taken in all subjects 1 year after last injection (at V05 + 12M). BL10 is to be taken in subjects from subgroup b 2 years after last injection (at V05 + 24M). BL7 through BL9 are taken in subgroup a only; and BL11 through BL13 are taken in subgroup b only.
- §§ Solicited injection site reactions will be collected for 7 days after injection. Solicited systemic reactions will be collected for 14 days after injection. Unsolicited AEs will be collected for 28 days after injection.
- *** DC4 will be provided to subgroup a to collect the full safety information after booster injection at Y1. DC4 Group b will be provided to subgroup b to collect SAEs from V07 Y1 to V07 Y2. DC5 will be provided to subgroup b to collect full safety information after booster injection at Y2. Dengue seronegative subjects at baseline from both subgroups will be provided with MA2.
- ††† Serious AESIs will be reported after each injection in defined time windows as follows: serious hypersensitivity/allergic reactions occurring within 7 days, serious viscerotropic disease occurring within 30 days, serious neurotropic disease occurring within 30 days; hospitalized suspected dengue disease will be reported during the entire study. Non-serious AESIs (ie, hypersensitivity / allergic reactions) will be reported within 7 days after each injection.
- ‡‡‡ At these time points, Ab specificity may be assessed, if necessary; Ab affinity maturation will not be assessed.

Table of Procedures – Phone Contacts

	STAGE I									STAGE II					
Phone Contact (PC)	PC1	PC2	PC3	PC4	PC5	PC6	PC7*	PC8	PC9	PC10	PC11	PC12*	PC13†	PC14†	PC15†
Trial timelines (Days/Months)	V01+ 2M	V01+ 4M	V01+ 8M	V01+ 10M	V01+ 14M	V01+ 16M	V01+ 18M	V01+ 20M	V01+ 22M	V05 + 14M	V05 + 16M	V05 + 18M	V05 + 20M	V05 + 22M	V05 + 30M
Time Windows (Days)	+8d	+8d	+8d	+8d	+8d	+8d	+20d	+8d	+8d	+8d	+8d	+8d	+8d	+8d	+20d
Ask about SAEs not yet reported‡	√	√	√	√	√	√	√	√	√	√	√	√	√	√	√

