 - 13) **For AIT subset only (60 subjects):** an additional volume of blood will be drawn (25 mL for adolescents and 35 mL for adults) to assess CMI (see [Section 7.1.2](#) for detailed instructions regarding the handling of CMI blood samples)

It is important to note that, if the attempt(s) to collect blood is (are) unsuccessful, the subject should be given the opportunity for another attempt, even on another day. If ultimately a blood sample cannot be obtained, the reason will be recorded in the eCRF. In that case, and if the subject wants to participate in the trial, he/she will be vaccinated.

- 14) Inject the appropriate study vaccine
- 15) Record the date of injection, the site and side of injection and the route of administration, as well as the dose number of the vaccine
- 16) Affix the vaccine labels in the subject's source documents
- 17) Keep the subject under observation for 30 minutes, and record any adverse reaction in the source documents
- 18) Give the subject / subject's parent (s) / legally acceptable representative(s) the diary card 1 (DC1) to record any injection site reactions and systemic AEs, together with

^a To be considered of non-child-bearing potential, a female must be post-menopausal for at least 1 year, surgically sterile, or using an effective method of contraception or abstinence from at least 4 weeks prior to vaccination and until at least 3 weeks after vaccination

instructions for its completion, including explanations on the definition and use of intensity scales for collection of AEs (Remind the parent / legally acceptable representative to bring back the DC when they return for Visit 02 at a specified date)

- 19) Give the subject / subject's parent (s) / legally acceptable representative(s) a ruler to measure the size of any injection site reaction and a thermometer for temperature measurement, and instructions on how to use them
- 20) Remind the subject / subject's parent (s) / legally acceptable representative(s) to call the study center if a serious medical event occurs
- 21) Arrange an appointment for the second visit (28 days [+ 14 days])
- 22) Complete the source documents and relevant eCRF pages for this visit

The visit may be postponed once if the subject is temporarily not eligible at Visit 1

Visit 2 (28 days [+14-day time window] after Visit 1): Collection of Safety Information

The Investigator or designated study personnel will:

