- 1) Perform a physical examination and record the subject's axillary temperature
- 2) Collect and check the information entered into the DC1 by interviewing the subject / subject's parent (s) / legally acceptable representative(s) and request information concerning any medical event, serious or not, that may have occurred since Visit 1
- 3) Check concomitant medications and record every reportable medication
- 4) Remind the subject / subject's parent(s) / legally acceptable representative(s) to call the study center if a serious medical event occurs
- 5) Arrange an appointment for Visit 3 (365 days [+/- 20 days] after Visit 1)
- 6) Complete the source documents and relevant CRF pages for the visit

Telephone Calls 1 and 2 (2 months and 4 months [+ 8 day window] after Visit 1)

The Investigator or authorized designee will:

- 1) Ask if the subject has experienced any SAEs not yet reported. If an SAE occurred, follow the instructions in [Section 10](#) for reporting it
- 2) Remind the subject / parent / legally acceptable representative to notify the site in case of an SAE

Visit 3 (180 Days [± 20-day Window] After Visit 1)

The Investigator or designated study personnel will:

- 1) Perform a physical examination and record the subject's axillary temperature
- 2) Review for any contraindications
- 3) Perform a urine pregnancy test (pre-injection) (women of childbearing potential only)
- 4) Check concomitant medications and record every reportable medication ongoing at the time of vaccination

- 5) **For all subjects:** collect the blood sample (BL2, 5 mL) for neutralizing Abs and record the date of collection (see [Section 7.1.1](#) for detailed instructions on the handling of blood samples)

Note: If the attempt(s) to collect blood is (are) unsuccessful, the subject should be given the opportunity to return to the study site for another attempt within the visit window. If a blood sample cannot be obtained, the reason will be recorded in the blood sampling page of the eCRF.

- 6) Contact IVRS/IWRS to obtain the dose number to be administered
- 7) Inject the appropriate study vaccine into the opposite limb from the limb the vaccination was administered to in Visit 1
- 8) Record the date of injection, the site and side of injection and the route of administration, as well as the dose number of the vaccine
- 9) Affix the vaccine labels in the subject's source documents

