- 5) **For AIT subset only (60 subjects):** an additional volume of blood will be drawn (25 mL for adolescents and 35 mL for adults) to assess CMI (see [Section 7.1.2](#) for detailed instructions regarding the handling of CMI blood samples).

For subjects from subgroup a:

- a. Review for any contraindications, including dengue serostatus at baseline
- b. Perform a physical examination and record the subject's axillary temperature
- c. Urine pregnancy test (pre-injection) (women of childbearing potential only)

- d. Check concomitant medications and record every reportable medication ongoing at the time of vaccination
 - e. Contact IVRS/IWRS to obtain the dose number to be administered
 - f. Inject the appropriate study vaccine into the opposite limb from the limb the vaccination was administered to in Visit 5
 - g. Record the date of injection, the site and side of injection and the route of administration, as well as the dose number of the vaccine
 - h. Affix the vaccine labels in the subject's source documents
 - i. Keep the subject under observation for 30 minutes, and record any injection site reactions or systemic events in the source documents and any reportable concomitant medications
- 6) For subgroup a: Give the subject / subject's parent (s) / legally acceptable representative(s) the DC4 to record any injection site reactions and systemic AEs, together with instructions for its completion, including explanations on the definition and use of intensity scales for collection of AEs.
- For subgroup b: Give the subject / subject's parent (s) / legally acceptable representative (s) the DC4 Group b to collect SAEs until the V07 (Y2) visit
- Dengue seronegative subjects at baseline: Give the subject / subject's parent (s) / legally acceptable representative(s) the MA2
- 7) Remind the parent / legally acceptable representative to bring back the DC4 or the DC4 Group b when they return for the next visit at a specified date
 - 8) Remind the subject /subject's parent(s) / legally acceptable representative(s) to call the study center a serious medical event occurs
 - 9) Arrange an appointment for the next visit (V08 for subgroup a AIT subset; V10 for other subgroup a subjects; V07 Year 2 for subgroup b subjects)
 - 10) Complete the source documents and relevant eCRF pages for this visit

Visit 7–Year 2 (24 Months [+60-day Window] After Visit 5): Booster Vaccination, Collection of Safety Information, and Blood Sample

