5.2.5 Exclusion Criteria

An individual fulfilling *any* of the following criteria is to be excluded from trial enrollment:

- 1) Subject is pregnant, or lactating, or of childbearing potential (to be considered of non-childbearing potential, a female must be pre-menarche^a, surgically sterile, or using an effective method of contraception or abstinence from at least 4 weeks prior to the first vaccination until at least 4 weeks after the last vaccination)
- 2) Participation at the time of study enrollment (or in the 4 weeks preceding the first trial vaccination) or planned participation during the present trial period in another clinical trial investigating a vaccine, drug, medical device or medical procedure
- 3) Self-reported or suspected congenital or acquired immunodeficiency; or receipt of immunosuppressive therapy such as anti-cancer chemotherapy or radiation therapy within the preceding 6 months; or long-term systemic corticosteroid therapy (prednisone or equivalent for more than 2 consecutive weeks within the past 3 months)
- 4) Self-reported systemic hypersensitivity to any of the vaccine components^b, or history of a life-threatening reaction to the vaccine used in the trial or to a vaccine containing any of the same substances
- 5) Chronic illness that, in the opinion of the Investigator, is at a stage where it might interfere with trial conduct or completion^c
- 6) Receipt of blood or blood-derived products in the past 3 months, which might interfere with assessment of the immune response
- 7) Planned receipt of any vaccine in the 4 weeks following any trial vaccination
- 8) Previous vaccination against dengue disease with either the trial vaccine or another vaccine
- 9) Deprived of freedom by an administrative or court order, or in an emergency setting, or hospitalized involuntarily

^a For pre-menarche females, young female subjects will declare if they have not yet started menstruation; if a young female subject reaches menarche during the study, she is to be considered as a woman of childbearing potential from that time forward.

^b The components of CYD dengue vaccine and placebo are listed in [Section 6.1](#) and in the Investigator's Brochure.

^c Chronic illness may include, but is not limited to, cardiac disorders, renal disorders, auto-immune disorders, diabetes, psychiatric disorders, or chronic infection.

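### Read literally, the definition attached to the urine pregnancy test exempts women who maintain contraception or abstinence from testing before the live booster, and other protocol text points the other way

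*Protocol*

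**What the plan says.** The steps for Visit 7–Year 1 and Visit 7–Year 2 in Protocol 5.1.4 both list "Urine pregnancy test (pre-injection) (women of childbearing potential only"). Visit 5 has the same words. Visit 3 says "Perform a urine pregnancy test (pre-injection) (women of childbearing potential only"), and Visit 1 says the same with a footnote marker on the term for childbearing potential.

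The definition stands in three places. In the Protocol Table of Procedures, the row "Urine Pregnancy Test (pre-injection") carries footnote **, which begins "Urine pregnancy test for females of child-bearing potential; to be considered of non-child-bearing potential". Visit 1 footnote a in Protocol 5.1.4 gives the same categories: "a female must be post-menopausal for at least 1 year, surgically sterile, or using an effective method of contraception or abstinence", from at least four weeks before to at least three weeks after vaccination. SAP Table 3.1 repeats the table footnote.

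Exclusion criterion 1 (Synopsis and Protocol 5.2.5) bars anyone who fits "Subject is pregnant, or lactating, or of childbearing potential". It treats as non-childbearing those who are pre-menarche, or "surgically sterile, or using an effective method of contraception or abstinence from at least 4 weeks prior to the first vaccination" to at least four weeks after the last one.

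Other text uses the term more widely. Footnote a of Protocol 5.2.5 says of a girl who reaches menarche on study that "she is to be considered as a woman of childbearing potential from that time forward". Protocol 5.2.7.2 makes pregnancy a definitive contraindication and identifies it by a positive urine test. Protocol 5.2.12 accepts that pregnancy may occur during participation and stops further vaccination when it does.

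**The concern.** The same phrase does two jobs. In criterion 1 it decides who may enroll, and there it is reasonable to count reliable contraception as enough. In the testing instruction it decides who is checked for pregnancy before an injection. The purpose of that check is to find the pregnancy that contraception failed to prevent. Carrying the enrollment meaning into the testing rule removes the check from the women for whom it is useful.

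The booster is a live attenuated vaccine (Protocol 6.1.1), given one or two years after Injection 3. A contraceptive failure that the woman has not noticed would be found at that visit mainly by the test. The matter is subject safety and clarity of instruction; it does not bear on power, error rates or any estimate.

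**Working it through.** The plan states no figure to reproduce. The check is mainly a comparison of texts, followed by a bound on the number of tests.

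**1. Who is enrolled.** Under criterion 1, an enrolled post-menarche woman is either surgically sterile or using contraception or abstinence.

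**2. Apply the test definition.** Both categories appear in footnote ** and Visit 1 footnote a as non-childbearing. While she maintains contraception or abstinence, such a woman is outside the tested group. The Visit 7 steps have no footnote of their own; the definition reaches them through those two footnotes.

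**3. Who is left to test.** Only women whose contraception or abstinence has lapsed, and girls who reach menarche on study. Even for these girls the texts conflict: 5.2.5 footnote a makes no exception for contraception, while the test definition does.

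**4. Is there an overriding rule?** Neither document says that contraception or abstinence users must be tested. The two definitions also differ elsewhere: three against four weeks after vaccination, with post-menopausal women listed only in one and pre-menarche girls only in the other.

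**5. Other checks at the booster.** The Table of Procedures schedules the inclusion/exclusion review at V01 only. Visit 7 calls for a contraindication review, but the listed contraindications (5.2.7.1, 5.2.7.2) do not include lapsed contraception and recognize pregnancy only by a positive urine test. No Visit 7 step explicitly re-checks contraception.

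**6. Which injections can still be affected.** The planned calendar (Protocol 5.1.5) is approximate.
- Earliest V05: 26 April 2016 + 345 days = 6 April 2017.
- Latest V05: 31 August 2016 + 385 days = 20 September 2017.
- The amended protocol refers to December 2017 (Section 1.2), so the primary injections are past.
- Year 1 boosters (V05 + 12 months, + up to 60 days): 6 April to 19 November 2018.
- Year 2 boosters (V05 + 24 months, + up to 60 days): 6 April to 19 November 2019.

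**7. Upper bound on tests.** The Synopsis estimates 630 to 735 subjects eligible for a booster. Two shares are assumed, because the documents give neither: 40–60% female, and 60–80% of those post-menarche, not sterile, not post-menopausal and admitted through contraception or abstinence.
- Low: 630 × 0.40 × 0.60 = 151.
- High: 735 × 0.60 × 0.80 = 353.
- At 50% female: 630 × 0.50 × 0.60 = 189 to 735 × 0.50 × 0.80 = 294.
- After the planned 15% dropout: 151.2 × 0.85 = 129 to 352.8 × 0.85 = 300.
- If boosters were given in one country only, with subjects split evenly (a further assumption): about 76 to 176.

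Every figure still includes women who have lapsed by the booster. They are tested even on the literal reading, so the true number is lower.

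**The case against.** The strongest reply is that the literal reading defeats the protocol's own purpose. If contraception users are not tested, the Visit 1 test decides nothing, since anyone tested would already be excluded. Yet a test is scheduled before every injection, and a positive result stops vaccination. Also, a contraception period running to three weeks after vaccination cannot be complete at a pre-injection test. The coherent intent is to test non-sterile post-menarche women, which would leave only a loosely worded footnote. This stands as an account of intent. It does not supply a rule: the only definition attached to the test gives the less safe answer, and nothing overrides it.

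A second reply is that other safeguards apply: contraception as an entry condition, physical examination and contraindication review at the visit, and no further vaccination in a known pregnancy. These are real, but for an unrecognized pregnancy the listed contraindication depends on the test.

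Third, several post-booster analyses in SAP 5.1.3 are limited to Colombia. The SAP does not say why, but boosters may have been fewer than the protocol's estimate. This stands, and is one reason to treat the count as a ceiling.

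A reader might infer that sites are omitting tests or behaving differently from one another. The documents report neither, and the Operating Guidelines, which are not available here, may settle the matter. A reader might also take 150 to 350 as women exposed in pregnancy. It is only a ceiling on injections without a required test; the documents support no estimate of missed pregnancies.

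**Conclusion.** The point holds as a conflict in the protocol's wording with a safety consequence. Read literally, post-menarche, non-sterile women who maintain contraception or abstinence need no pregnancy test before the live booster, although 5.2.5 footnote a and 5.2.7.2 suggest that the sponsor meant more. It is more than missing detail, because the written rule is present and leads the wrong way.

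Its size is uncertain. The ceiling of about 150 to 350 booster tests rests on the protocol's eligibility estimate and on the assumed sex and menarche shares; lapsed users, dropouts, fewer boosters and sites already testing all lower it. The documents do not support saying that every woman admitted through contraception is exempt, since a lapsed user falls back into the tested group. No endpoint or analysis is affected.

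**What to change.** In Table of Procedures footnote ** and Visit 1 footnote a of Protocol 5.1.4, define the group to be tested as all females past menarche who are neither surgically sterile nor at least one year past menopause, whatever contraception they use. State at Visit 7–Year 1 and Visit 7–Year 2 that this definition applies before the booster.

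Leave criterion 1 as it is: enrollment is closed, and contraception or abstinence can remain an entry condition. Align the footnote in SAP Table 3.1 for consistency only; it does not direct what sites do.

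The cost is the wording of two protocol footnotes, a line at each booster visit and the SAP copy, plus urine tests of a kind already scheduled, within the ceiling given above. A site that already tests these women adds none.
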